Day 8	Predose	Within 1 hour before Day 8 dose	Predose	Within 1 hour before Day 8 morning dose
	Predose	Within 1 hour before Day 15 dose	Predose	Within 1 hour before Day 15 morning dose
	2 hours ^c	±10 minutes	-	-
Day 15	6 hours	±30 minutes	6 hours	±30 minutes
Cycle 2, 3 and 4				
Day 1	Predose	Within 1 hour before Day 1 dose	Predose	Within 1 hour before Day 1 dose
EOT	X	Any time during visit	X	Any time during visit

Abbreviations: EOT = end of treatment, PK = pharmacokinetic(s).

a For samples collected for both SAR442720 and adagrasib can be collected at the same time points.

b Windows are relative to the nominal time point.

c SAR442720 only PK samples.

Table 8 - PK time points for Part-4

SAR442720			Pembrolizumab		
Study Day	PK Time points ^a	Window ^b	Study Day	PK Time points ^a	Window ^b
Cycle 1					
Day 1	Predose ^c	Within 1 hour before Day 1 dose	Day 1	Predose ^c	Within 1 hour before Day 1 dose
	0.5 hour	±5 minutes			
	1 hour	±10 minutes			
	2 hours	±10 minutes			
	4 hours	±30 minutes			
	8 hours	±30 minutes			
Day 2	24 hours post Day 1 dose	Within 1 hour before Day 2 dose	-	-	-
Day 8	Predose	Within 1 hour before Day 8 dose	-	-	-
Day 15	Predose ^c	Within 1 hour before Day 1 dose	-	-	-
	0.5 hour	±5 minutes			
	1 hour	±10 minutes			
	2 hours	±10 minutes			
	4 hours	±30 minutes			
	8 hours	±30 minutes			
Day 16	24 hours post Day 15 dose	Within 1 hour before Day 16 dose	-	-	-
Cycle 2					
Day 1	Predose ^c	Within 1 hour before Day 1 dose	Day 1	Predose ^c	Within 1 hour before Day 1 dose
	0.5 hour	±5 minutes			
	1 hour	±10 minutes			
	2 hours	±10 minutes			
	4 hours	±30 minutes			
	8 hours	±30 minutes			
Day 2	24 hours post Day 1 dose	Within 1 hour before Day 2 dose	-	-	-
Cycle 6					
Day 1	Predose ^c	Within 1 hour before Day 1 dose	Day 1	Predose ^c	Within 1 hour before Day 1 dose
EOT	X	Any time during visit	-	-	-

Abbreviations: EOT = end of treatment; PK = pharmacokinetic(s).

a PK samples = one 1.5 mL sample is required per time point.

b Windows are relative to the nominal time point.

c PK samples for SAR442720 and pembrolizumab will be collected at the same time points.

Table 9 - Pharmacodynamic/biomarker sampling time points (Part-1 and Part-2)

Study Day	RNA Biomarker Time points ^a	Blood germline testings ^b	ctDNA Biomarker Time points ^c	Immune cell profiling time points ^d	Cytokines time points ^e	Window ^f
Cycle 1						
Day 1	Predose	Predose	Predose	Predose	Predose	Within 1 hour before Day 1 dose
Day 15	Trough		Trough	Trough	Trough	

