8.4 TREATMENT OF OVERDOSE

The Sponsor does not recommend specific treatment for an overdose (defined in [Section 8.3.6](#)).

In the event of an overdose, the Investigator should:

1. Contact the Medical Monitor immediately.
2. Closely monitor the participant for any AE/SAE and laboratory abnormalities until SAR442720 can no longer be detected systemically (at least 5 days).
3. Obtain a plasma sample for PK analysis within 1 to 2 days from the date of the last dose of study intervention if requested by the Medical Monitor (determined on a case-by-case basis).
4. Document appropriately in the CRF.

Decisions regarding dose interruptions or modifications will be made by the Investigator in consultation with the Medical Monitor based on the clinical evaluation of the participant.

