## 4.8 OTHER ANALYSES

### 4.8.1 PK analyses

Concentrations of SAR442720, pembrolizumab and adagrasib will be summarized by scheduled visit and nominal timepoint.

All concentration values below the lower limit of quantitation (LLOQ) will be treated as zero in all summary statistics excepted for the geometric mean and associated coefficient of variation for which they will be considered as missing.

For Part-3A and Part-4, PK parameter estimates, including but not limiting to the ones listed below, will be determined when possible, for SAR442720 and adagrasib:

- Maximal concentration: Cmax (observed)
- Time to reach maximal concentration: Tmax (observed)
- Area-under-the-curve from time 0 to t: AUC0-t
- Area-under-the-curve from time 0 to infinity, if possible: AUC0-inf, if possible
- t1/2, if possible
- Accumulation ratio

Unless otherwise specified, the PK parameters will be estimated based on noncompartmental analysis methods. These estimates will be summarized descriptively by dose cohort. All PK parameters will be computed using the actual elapsed time calculated relative to dose administration.

[figure not shown]
For Part-4, the geometric mean ratios and 90% confidence intervals of AUC0-inf and Cmax will be computed for SAR442720 between fed and fasted states of tablet formulation (C1D1 to C1D15) and between the tablet (test) and capsule (reference) formulations (C1D15 to C2D1). In addition, the PK parameters in Part-4 will be analyzed using a mixed effect model, which will be described in detail in the statistical analysis plan.

Population PK analysis may be conducted to obtain the PK parameters of SAR442720, pembrolizumab, and adagrasib. If performed, the results will be summarized in a separate report. Exploratory analyses may be performed to evaluate the relationship between the estimated PK parameters and PDs, selected safety, biomarker, or clinical effect endpoints.

The PK and PDy analyses will be presented in a separate report.

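### Part-4: both primary exposure ratios use an AUC extrapolated past the last sample (24 h), with no ratio secured for the observed AUC; SAP 2 states precision per group for a one-group design

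*SAP*

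**What the plan says.** **Ratios.** SAP 4.8.1 computes "the geometric mean ratios and 90% confidence intervals of AUC0-inf" and Cmax for fed versus fasted tablet (C1D1, C1D15) and for tablet versus capsule (C1D15, C2D1). Its parameter list also contains AUC0-t, and it makes the extrapolated AUC conditional: "Area-under-the-curve from time 0 to infinity, if possible: AUC0-inf, if possible". A mixed-effect model of the PK parameters is promised, "which will be described in detail in the statistical analysis plan". That sentence is itself in the SAP, and no model is written out.

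**Sampling.** Protocol 1.3, Table 8 takes samples before the dose and at 0.5, 1, 2, 4, 8 and 24 h for each of the three profiles. The C1D15 profile, for example, ends with the sample "24 hours post Day 15 dose", whose window is "Within 1 hour before Day 16 dose".

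**Endpoints.** The Part-4 primary endpoints in Protocol 3 (Table 12) and SAP 1.2 (Table 2) give AUC0-last as the example AUC. Protocol 9.4.4 says only AUC for the ratios and lists both AUC0-t and AUCinf.

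**Precision.** SAP 2 states Part-4 precision for 12 enrolled and 9 evaluable participants per group, from a single-dose AUC CV. SAP 1.1 gives about 12 participants overall. Protocol 4.1 and 4.2 describe a fixed sequence in which the same participants receive every condition. Protocol 9.2 bases precision on the intra-subject variability of steady-state AUC. The CVs and the resulting precision are redacted in both documents.

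**The concern.** The two ratios are the main comparisons for the two Part-4 primary objectives. Their only AUC depends on a terminal slope that must be estimated from few late samples, with none between 8 and 24 h, and on an area after the last sample. If the slope is poorly determined, the ratio becomes noisier or is missing for some participants. The Part-4 PK-evaluable set in SAP Table 3 does not require an estimable AUC0-inf, so a participant can count towards the 9 evaluable and still contribute no AUC ratio. The observed AUC has neither problem, but no ratio or 90% CI is secured for it.

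The SAP 2 wording describes a different design. What matters there is the kind of CV. If the single-dose CV is a between-participant figure, the stated precision does not describe a within-participant comparison.

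**Working it through.** **The plan's own figure.** The Part-4 precision cannot be reproduced because both the CV and the result are redacted. Everything below uses assumed inputs.

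**1. Share of AUC0-inf after 24 h.** With mono-exponential decline the share is 2^(-24/t½).

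| Assumed half-life | Share beyond 24 h |
|---|---|
| 8 h | 12.5% |
| 12 h | 25% |
| 17 h | 38% |
| 24 h | 50% |

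It passes 20% at about 10.3 h.

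**2. Extra noise from extrapolation.** I simulated 40,000 one-compartment oral profiles at the Table 8 times. Assumptions: absorption rate 1/h, 15% log-normal residual error, linear-up/log-down AUC, terminal slope from the 4, 8 and 24 h samples.

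| Half-life | SD of log AUC0-24 | SD of log AUC0-inf |
|---|---|---|
| 8 h | 0.078 | 0.081 |
| 12 h | 0.080 | 0.116 |
| 17 h | 0.082 | 0.199 |
| 24 h | 0.082 | 0.364 |

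**3. Effect on the ratio.** These SDs are residual error only, so they have to be added to the intra-subject variation.
- Assumed CV 30%: σ_w = √ln(1 + 0.30²) = 0.294.
- Half-width on the log scale, one-group model with three conditions, n = 12: t(0.95, 22) × σ × √(2/12) = 1.717 × 0.294 × 0.408 = 0.206.
- With extrapolation, replace σ_w² by σ_w² + (SD²_inf − SD²_0-24). At 12 h: 0.0862 + 0.116² − 0.080² = 0.0932, so σ = 0.305.

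| Half-life | Log half-width, AUC0-inf | Change from 0.206 |
|---|---|---|
| 8 h | 0.206 | none |
| 12 h | 0.214 | +4% |
| 17 h | about 0.24 | about +17% |
| 24 h | about 0.32 | about +55% |

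For n = 9 evaluable the starting half-width is 0.242.

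**4. Per group versus one group.** Two parallel groups of n have standard error σ√(2/n) and 2n − 2 degrees of freedom. The one-group, three-condition model has the same standard error and 2(n − 1) degrees of freedom, which is the same number. At CV 30% and n = 12 both give 0.206; a simple paired comparison (11 degrees of freedom) gives 0.215. At equal CV the wording therefore barely matters. The type of CV does matter. If the intra-subject CV were 20% and the total CV 40%, a paired interval around 1 with n = 12 would be 0.865 to 1.156, and a two-group interval from the total CV 0.763 to 1.310.

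**5. Cost of stopping at 24 h.** If food only halved the absorption rate (1 to 0.5/h) at the same extent, the AUC0-24 ratio would be (1 − 0.151)/(1 − 0.137) = 0.98 at a half-life of 8 h and (1 − 0.531)/(1 − 0.515) = 0.97 at 24 h, instead of 1.00.

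**The case against.** The strongest reply is that no harm is shown. The documents give no half-life, and at 8 h the choice of AUC makes no practical difference. AUC0-t is still estimated and summarised, and it may enter the mixed model. The protocol's ratio wording allows either AUC. Part-4 tests no hypothesis, and Protocol 4.2 calls the food assessment preliminary. Most of this stands, and it limits the size of the point. It does not supply a fallback, and it does not secure a ratio for the AUC that the sampling can always deliver.

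Five stronger readings are tempting, and the documents do not support them:
- **A long half-life is known.** Protocol 8.4 asks for monitoring after an overdose "until SAR442720 can no longer be detected systemically (at least 5 days". That is a minimum monitoring period after an excess dose. Turning it into 12, 17 or 24 h requires assuming that it spans 10, 7 or 5 half-lives.
- **The ratio becomes four times noisier.** The residual-error SDs at 24 h differ by about that factor (0.364 against 0.082), but once intra-subject variation is included the half-width grows by about 55%.
- **Half the participants would be lost.** No extrapolation cut-off is stated. In the simulation a non-positive terminal slope was practically absent up to 17 h and occurred in about 0.2% of profiles at 24 h.
- **The SAP departs from the protocol.** Protocol 9.4.4 does not specify which AUC, and the endpoint tables offer AUC0-last only as an example.
- **The stated precision is wrong.** The figures are redacted, and per-group wording alone barely moves them.

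**Conclusion.** The point holds as a mismatch between analysis and sampling. The only AUC with a planned ratio is the one that SAP 4.8.1 itself treats as possibly not estimable, while the observed AUC named in the endpoint tables has no planned ratio or interval. The loss of precision is nil to slight for half-lives up to 12 h and becomes material only from about 17 h, under the one-compartment model, 15% residual error and 30% intra-subject CV assumed here. The documents do not show which case applies.

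The SAP 2 wording conflicts with SAP 1.1 and with Protocol 4.1, 4.2 and 9.2. Its numerical effect depends on whether the single-dose CV is within or between participants, which is not stated. Taken together this is a minor to moderate correction that affects how reliable and how clearly described the estimates are. No error rate is involved.

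**What to change.** **SAP 4.8.1.** Compute both geometric mean ratios and 90% CIs for AUC over the observed interval and for Cmax. Use a common 0-24 h interval in the conditions compared. This needs saying because "All PK parameters will be computed using the actual elapsed time calculated relative to dose administration" and the last sample may be taken up to an hour before the next dose, so AUC0-last could end at different times in the two conditions. Keep AUC0-inf as supportive where it is reliably estimable, and state the criterion.

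Write out the mixed model here: the same log-transformed parameters, condition (fed tablet, fasted tablet, fasted capsule) as a fixed effect, participant as a random effect, in the PK-evaluable set of SAP Table 3.

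**SAP 2.** State about 12 participants in total (9 evaluable), each giving all three conditions. Base the precision on the intra-subject CV, and reconcile the single-dose input with the steady-state input of Protocol 9.2.

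**Cost.** SAP wording and a few outputs, with no new samples or participants. The stated precision may change. AUC0-24 leaves out exposure after 24 h, so delayed absorption alone could make the fed/fasted ratio read about 0.97 to 0.98; this is the reason to keep AUC0-inf alongside it.

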Diarrhea	
Diarrhea AEs, of any grade, were reported in 48.7% (55/113) participants in the RMC-4630-01 study. Grade ≥3 AEs were reported in 5.3% (6/113) participants. Median time to onset of diarrhea was 9.0 days from the start of study treatment and median duration was 4.0 days.
 
Guidance to the Investigators:
 
Evaluate for other or concomitant causes, including medications (eg, stool softeners, laxatives, antacids), infection including Clostridium difficile, malabsorption/lactose intolerance, fecal impaction, and dietary supplements high in fiber.
 
For Grade 1 or 2 diarrhea, dietary modifications should be considered including cessation of lactose-containing products, eats small meals, and adequate hydration. Consumption of the BRAT (banana, rice, apples, toast) diet may be helpful. In addition, loperamide or codeine may be used or alternatives in refractory cases such as octreotide and budesonide.
 
For >Grade 2 diarrhea, consider hospitalization for fluid and electrolyte replacement and antibiotics, particularly if accompanied by fever or Grade 3-4 neutropenia.
 
Consultation with a gastroenterologist should be considered, particularly for severe or refractory events.

Anemia*	
Anemia AEs of any grade were reported in 37.2% (42/113) participants in the RMC-4630-01 study. Grade ≥3 AEs were reported in 16.8% (19/113) participants. Median time for onset of anemia*** was 21.5 days and median duration was 21.5 days.
 
Guidance to the Investigators:
 
Monitor closely and provide supportive care according to institutional standards. Interrupt study treatment as clinically appropriate. Dose interruption or discontinuation may not be required depending on baseline hemoglobin and transfusion history.

* Includes edema peripheral, pleural effusion, periorbital edema, face edema, pericardial effusion, localized edema, peripheral swelling, ascites, generalized edema, eyelid edema, fluid retention, joint swelling, lip edema, and pulmonary edema; thrombocytopenia includes thrombocytopenia and platelet count decreased, anemia includes anemia, anemia macrocytic, hemoglobin decreased, and normocytic anemia

** Time to and duration of thrombocytopenia was calculated using laboratory data.

*** Time to and duration of anemia was calculated using laboratory data.

Thromboembolic events:

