Primary 
To evaluate the impact of food on the PK of SAR442720 when dosed in combination with pembrolizumab.To evaluate the impact of the formulation (tablets vs. capsules) on the PK of SAR442720 when dosed in combination with pembrolizumab.	
Plasma PK parameters of SAR442720 following oral administration of SA442720 tablets in combination with pembrolizumab under fed and fasted states (eg, C_{max}, T_{max}, AUC_{0-last}).Plasma PK parameters of SAR442720 following oral administration of SAR442720 tablets (test formulation) and capsules (reference formulation) in combination with pembrolizumab under fasted state (eg, C_{max}, T_{max}, AUC_{0-last}).
Secondary 
To assess the safety and tolerability of SAR442720 under fasted and fed conditions in combination with pembrolizumab through the cycles, when dosing with capsule and tablet formulations in combination with pembrolizumab.To estimate the anti-tumor effects of SAR442720 in combination with pembrolizumab in all participants.	
Incidence, nature, and severity of TEAEs and SAEs, graded according to the NCI CTCAE v5.0 for SAR442720 in combination with pembrolizumab.ORR and DoR of SAR442720 and pembrolizumab in all participants. ORR of combination therapy with SAR442720 and pembrolizumab will be based on RECIST v1.1.

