Part-3B aims to determine the anti-tumor activity of SAR442720 in combination with adagrasib in participants with NSCLC and KARAS G12C mutations, which can result in an increased ORR. The goal of the combination therapy approach is to expand the spectrum of patients who respond to targeted KRAS G12C therapy and to improve the quality of clinical responses (ie, durable response and prolonged PFS) beyond what can be achieved with monotherapy alone.

The design of the study is a non-randomized study in which the experimental combination will be assessed in a single cohort for each indication. The ORR will be assessed using RECIST v1.1. The objective response will be assessed by the Investigator in first intention. Central imaging reading may be done retrospectively if significant activity is observed.

Part-4 aims to assess the impact of formulation and preliminary impact of food on the PK of SAR442720 in combination with pembrolizumab. Part-4 is an open label, non-randomized fixed-sequence study, intending to assess preliminary effect of food on SAR442720 tablet and relative bioavailability of SAR442720 tablets versus capsules in participants with advanced malignancies. The PK of SAR442720 under fasted state will be served as the test treatment of formulation bridging; therefore, both the food effect and formulation effect can be assessed in the same participants, to reduce the number of participants needed.

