8.5 PHARMACOKINETICS

Plasma samples will be obtained for PK analysis of SAR442720 as outlined in the SoA (see [Section 1.3](#)). Concentrations at each time point will be reported.

- Whole blood samples of approximately 1.5 mL will be collected and processed into plasma for measurement of plasma concentrations of SAR442720 as specified in the SoA (see [Section 1.3](#)). Instructions for the collection and handling of biological samples will be provided by the sponsor. The actual date and time (24-hour clock time) of each sample will be recorded.
- Samples collected for analyses of SAR442720 plasma concentration may also be used for exploratory analysis, such as metabolic profiling of SAR442720.

Serum samples will be obtained for PK analysis of pembrolizumab as outlined in the SoA (see [Section 1.3](#)). Concentrations at each time point will be reported.

- Whole blood samples of approximately 1.5 mL will be collected and processed into serum for measurement of serum concentrations of pembrolizumab as specified in the SoA (see [Section 1.3](#)). Instructions for the collection and handling of biological samples will be provided by the sponsor. The actual date and time of each sample will be recorded. Pharmacokinetic samples will be tested by the Sponsor or Sponsor's designee.
- Samples collected for analyses of pembrolizumab serum concentration may also be used for other analysis, such as immunogenicity assessment.
- Plasma samples will be obtained for PK analysis of adagrasib as outlined in the SoA (see [Section 1.3](#)). Concentrations at each time point will be reported.
- Whole blood samples of approximately 1.5 mL will be collected and processed into plasma for measurement of plasma concentrations of adagrasib as specified in the SoA (see [Section 1.3](#)). Instructions for the collection and handling of biological samples will be provided by the Sponsor. The actual date and time of each sample will be recorded.
- For Part-3A and Part-4, the PK parameters of SAR442720 and adagrasib will be calculated using a non-compartmental method. The PK parameters (eg, C_{max} , time to achieve maximum concentration [T_{max}], area under the concentration–time curve from Time 0 to Time t [AUC_{0-t}], area under the concentration–time curve from Time 0 to infinity [AUC_{inf}], elimination half-life [$t_{1/2}$], if possible, and the accumulation ratio) of SAR442720 and adagrasib will be assessed for each evaluable participant.

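### Part-4's primary food-effect ratio compares a fed first dose with a fasted repeat dose, so Part-4 data alone cannot separate food from dose occasion, and residual drug is not removed

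*SAP*

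**What the plan says.** The first Part-4 primary objective is "To evaluate the impact of food on the PK of SAR442720 when dosed in combination with pembrolizumab" (Protocol Section 3). Protocol 4.2 describes the design: "Part-4 is an open label, non-randomized fixed-sequence study, intending to assess preliminary effect of food on SAR442720 tablet".

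Protocol 4.1 sets three conditions, all in the same order: tablet with breakfast on C1D1, tablet after an overnight fast on C1D15, capsule after an overnight fast on C2D1. SAR442720 is given on Days 1 and 2 of each week. Protocol Table 8 places full profiles, from predose to 24 h, on those three days only.

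For the analysis, SAP 4.8.1 states that ratios of AUC0-inf and Cmax with 90% intervals "will be computed for SAR442720 between fed and fasted states of tablet formulation (C1D1 to C1D15". Protocol 9.4.4 plans the same contrast but says only AUC; the endpoint tables give AUC0-last as the example. A mixed model is also promised, "which will be described in detail in the statistical analysis plan", but that sentence stands in the SAP itself and no model terms follow.

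The same SAP section introduces a parameter list with "For Part-3A and Part-4, PK parameter estimates, including but not limiting to the ones listed below, will be determined when possible, for SAR442720 and adagrasib". The list includes "Accumulation ratio" without naming days or a formula. Protocol 8.5 likewise says "and the accumulation ratio) of SAR442720 and adagrasib will be assessed for each evaluable participant".

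**The concern.** The fed profile is always the drug-naive profile, and the fasted tablet profile always follows four earlier doses. Whatever differs between Day 1 and Day 15 therefore enters the food ratio: residual drug, altered clearance, altered absorption. The SAP neither removes residual drug nor gives a reason to think it negligible, and it does not warn that the ratio mixes two things.

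The choice of AUC0-inf does not help. On C1D15 it counts drug left from earlier doses. It must also be extrapolated beyond 24 h on both days, because the next dose follows on Day 2 or Day 16. The SAP itself lists AUC0-inf only where it can be estimated.

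At stake is the meaning of a primary result: a ratio below 1 could be read as food lowering exposure when part or all of it is carry-over, and a real increase with food could be masked.

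**Working it through.** **Plan's own figure.** The Part-4 precision statement (Protocol 9.2, SAP Section 2) has its coefficient of variation (CV) and imprecision blacked out, so it cannot be reproduced.

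**Can a model separate the effects?** Code the three occasions (C1D1, C1D15, C2D1) as fed = (1, 0, 0), capsule = (0, 0, 1), repeat dose = (0, 1, 1). Then fed = 1 − repeat dose on every row. With an intercept the design matrix has rank 3 for 4 columns, and fed and repeat dose correlate at −1.0. No mixed model fitted to these occasions alone can estimate both.

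**What the ratio estimates.** Let F be the true fed/fasted ratio and A the Day 15/Day 1 exposure ratio at equal meal status. The reported ratio is F/A. For example, F = 1.25 with an assumed A = 1.20 gives 1.25/1.20 = 1.04.

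**Size from residual drug alone.** Inputs: doses on Days 1, 2, 8, 9 and 15 (Protocol 4.3, Part-4); half-life h not given, assumed 12 to 72 h; linear one-compartment bolus model; F = 1.00. The earlier doses precede C1D15 by 336, 312, 168 and 144 h, so

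A = 1 + 2^(−336/h) + 2^(−312/h) + 2^(−168/h) + 2^(−144/h).

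At h = 48: A = 1 + 0.0078 + 0.0110 + 0.0884 + 0.1250 = 1.232, and the reported ratio is 1/1.232 = 0.81.

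| Assumed half-life | A | Reported fed/fasted if food has no effect | C1D15 predose as % of Cmax (1 − 1/A) |
|---|---|---|---|
| 12 h | 1.000 | 1.00 | under 0.1% |
| 24 h | 1.024 | 0.98 | 2.3% |
| 36 h | 1.106 | 0.90 | 9.6% |
| 48 h | 1.232 | 0.81 | 18.8% |
| 72 h | 1.537 | 0.65 | 35% |

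With first-order absorption at 1/h instead, the ratios from 24 to 72 h are 0.98, 0.90, 0.80 to 0.81 and 0.64 to 0.65. In the bolus model AUC0-24, AUC0-inf and Cmax give the same ratio. Moving to AUC0-last therefore avoids extrapolation but does not remove the carry-over.

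**Scale against precision.** Take a 90% interval on the log scale with half-width w = t(0.95, n−1) × s × √(2/n), s = √ln(1 + CV²), and imprecision 1 − exp(−w). For n = 12 and an assumed CV of 20%, w = 1.796 × 0.198 × 0.408 = 0.145, so imprecision is 13.5%; at CV 30% it is 19.4%. For n = 9 the figures are 15.9% and 22.7%. A shift of 2% would be lost in this; one of 19% would be about as large as the interval's half-width.

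**Tablet versus capsule.** Both profiles are repeat doses. The C1D15/C2D1 ratio from residual drug alone is 0.999 at 48 h and 0.989 at 72 h, so this comparison is hardly touched.

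**The case against.** The best defence is that the design is open about itself. Protocol 4.2 calls it fixed-sequence and its food assessment preliminary, and gives saving participants as the reason. Protocol 9.1 plans no formal test. The last dose before C1D15 is on Day 9, which leaves 144 h; at a half-life of 24 h or less the carry-over is about 2% or less. The overdose guidance in Protocol 8.4 follows participants until the drug is undetectable, at least 5 days, which is compatible with small carry-over. All of this stands as a limit on size: a material bias is possible, not shown. It does not remove the aliasing, and the word preliminary appears neither in the Part-4 objectives nor in the SAP analysis.

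A reader might infer more than the documents support:

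- *That the accumulation ratio is the food ratio inverted.* It is defined nowhere. C1D15/C1D1 is the only same-formulation pair of full profiles, but Table 8 also has predose samples on Days 8 and 15 and on C2D1, so a trough ratio is open. The list also names adagrasib, which is not given in Part-4, so it does not apply item by item.
- *That the bias runs in one direction.* Residual drug lowers fed/fasted; impaired absorption by Day 15 would raise it; time-dependent clearance could do either.
- *That diarrhea shows an absorption change.* Protocol Table 11 does say "Median time to onset of diarrhea was 9.0 days from the start of study treatment", but the figures are from the monotherapy study, and the median duration was 4.0 days, so a typical episode ends before Day 15.
- *That no analysis could ever help.* The limit is Part-4 data alone. Part-1 has SAR442720 samples at 2 h and 8 h on C1D1 and C2D1, and population PK is foreseen.

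**Conclusion.** The point holds in this form: the planned food ratio cannot be separated from dose occasion within Part-4, and the SAP leaves residual drug in both AUC0-inf and Cmax. The aliasing follows from the schedule and needs no assumption. The size rests on an unstated half-life, linear kinetics and on-schedule dosing: negligible at 12 h, about 2% at 24 h, 10% at 36 h, 19% at 48 h and 35% at 72 h. The documents do not show which applies, and these figures cover residual drug only. The issue deserves correction because it affects a primary endpoint and the samples needed to examine the residual-drug part are already planned.

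**What to change.** 1. In SAP 4.8.1, prespecify that C1D15 and C2D1 profiles are corrected for residual drug, subtracting C_predose × exp(−λz × t) before deriving AUC and Cmax. Take a predose value below the quantification limit as zero. Report predose concentration as a percentage of Cmax; in the bolus model above this percentage equals the shift in the ratio. Compare AUC0-last over the sampled 24 h alongside AUC0-inf, with uncorrected values as sensitivity. Write out the mixed model in the same edit. Downside: the correction assumes linear kinetics, and λz comes from profiles ending at 24 h, so it is least reliable at the long half-lives where it matters most. It does not address changes in clearance or absorption.
2. Report the ratio as *fed first dose versus fasted repeat dose*, and state that food is not separable from dose occasion.
3. For Part-4, delete the accumulation ratio from Protocol 8.5 and 9.4.4 and SAP 4.8.1, or define it on predose troughs, for example Day 15/Day 8, and not as C1D15/C1D1. The Day 8 trough still contains some of the fed Day 1 dose and may be unquantifiable if the half-life is short. Do not substitute the Part-3A value: it is for capsules given with adagrasib, which Protocol 2.3.1.5 expects may raise SAR442720 exposure up to 2-fold.

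Cost: SAP text, matching protocol wording for item 3, and a little PK programming; no new samples or visits. If enrolment is open, alternating which of C1D1 and C1D15 is the fed day is an option, not a requirement. It needs an amendment, and for half the participants the fasted tablet profile in the tablet/capsule comparison would become the first dose.
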